4.7.2. Temperature and Arterial Oxygen Saturation

Temperature and arterial oxygen saturation will be summarized descriptively, including the number and percent of subjects with normal, abnormal, and clinically significant results at Baseline. All temperature and arterial oxygen saturation data for each subject will be provided in data listings.

Statistical Analysis Plan

Sponsor:	McMaster University		
Protocol:	TOGETHER trial		
Document Version No.:	1.1	Document Date:	05-May-2021

4.7.3. Electrocardiogram

ECG results will be summarized descriptively, including the number and percent of subjects with normal, abnormal and clinically significant abnormal results at Baseline. All ECG data for each subject will be provided in data listings.

4.7.4. Concomitant Medications

Concomitant medications will be coded using the WHO Drug dictionary. Results will be tabulated by Anatomic Therapeutic Class (ATC) and preferred term. The use of concomitant medications will be included in by-subject data listing.

4.7.5. Vaccination Status

Vaccination status will be tabulated and will be included in by-subject data listing. It may also be used in a sensitivity analysis.

APPENDIX

1. Interim analysis in an even-based Bayesian adaptive clinical trial

Suppose that we have I active treatments, such that

$$y_{ij}|p_i \sim \text{Binom}(n_{ij}, p_i), \quad i = 1, \dots, I,$$

where $j = 1, \dots, J$ denotes the number of interim analysis, n_{ij} is the number of patients randomized to the i^{th} arm, and p_i is the corresponding event rate. If we then assign a prior distribution

$$p_i \sim \text{Beta}(a, b),$$

Then by conjugation we obtain

$$p_i|y_{ij} \sim \text{Beta}(a + y_{ij}, b + n_{ij} - y_{ij}). \quad (1)$$

Control comparisons will then be based on *posterior efficacy*, namely

$$\Pr(p_i < p_{\text{ctrl}} | y_{ij}, y_{\text{ctrl}}),$$

which can be handily calculated by drawing independent Monte Carlo samples from the posterior distributions of the two arms using (1). Posterior inference on the relative risk reduction (RRR) can then be derived using the relationship

$$R_i = 1 - \frac{p_i}{p_{\text{ctrl}}}. \quad (2)$$

Proposed design for a 4-arm trial

- Perform interim analysis when 171, 342, and 513 patient outcomes have been recorded for each of the trial arms – corresponding to 25%, 50% and 75% of the maximum enrollment - and a final analysis when all 681 patient outcomes have been registered.
- Use $a = b = 1$ for beta prior distribution of all arms, corresponding to a uniform distribution.
- Stop early for efficacy if the posterior probability of efficacy exceeds 97.6%. The same test is conducted at the end of the trial if no early stopping rules are triggered.

Statistical Analysis Plan

Sponsor:	McMaster University		
Protocol:	TOGETHER trial		
Document Version No.:	1.1	Document Date:	05-May-2021

- Stop early for futility if the posterior probability of efficacy is smaller than 20% in the first analysis; 40% in the second analysis; 60% in the third analysis.

The operating characteristics of this design, as determined by 200,000 simulation runs, are as follows

Table 4: Operating Characteristics for the Proposed Bayesian Design

Arm	RRR	Power	Mean % of patients (SD)	Pr(Stop at 1)	Pr(Stop at <=2)	Pr(Stop at <=3)
1	37.50%	84.80%	64.1 (29.6)	25.20%	53.50%	73.80%
2	20%	30.70%	84.2 (26.0)	10.40%	23.90%	39.20%
3	0%	2.50%	71.1 (28.4)	16.80%	42.50%	67.00%

From Table 4 it is evident that the type I error rate of this trial design is 2.5% (one-sided). Note that a treatment with a relative risk reduction of 37.5% will – on average – require only two-thirds of the maximum sample size of 681.

The simulation run also allows us to evaluate the frequency of the reasons for early stopping under each scenario. The details are given in Table 2 and Figure 2.

Table 5: Distribution of the Causes for Early Stopping Under Various Scenarios

[figure not shown]
RRR	Stopping Reason	Analysis 1	Analysis 2	Analysis 3	Analysis 4
0%	Early efficacy	1.00%	0.30%	0.20%	0.00%
	Futility	15.80%	23.50%	18.00%	0.00%
	None	0.00%	1.90%	6.40%	32.90%
20%	Early efficacy	6.70%	6.90%	4.90%	0.00%
	Futility	3.60%	4.70%	4.10%	0.00%
	None	0.00%	1.80%	6.30%	60.90%
37.5%	Early efficacy	24.70%	26.40%	15.30%	0.00%
	Futility	0.50%	0.20%	0.20%	0.00%
	None	0.00%	1.70%	4.90%	26.20%

Statistical Analysis Plan

Sponsor:	McMaster University		
Protocol:	TOGETHER trial		
Document Version No.:	1.1	Document Date:	05-May-2021

Figure 2: a graphical illustration of Table 2.

Example: a simulated 4-arm trial

To illustrate the application of the decision rules in the proposed design, we drew one instance of the data according to the 15% control event rate and the specified effect sizes. The resultant trial consisted of 4 analyses: three interim analyses and one final analysis. Table 3 monitors the cumulative number of events over time for each arm. Note that already at the first interim look, arm 3 was dropped due to hitting a futility rule after 171 patient outcomes were observed. Two analyses and 342 patients later, arm 1 crossed the efficacy threshold, following which no more

Statistical Analysis Plan

Sponsor:	McMaster University		
Protocol:	TOGETHER trial		
Document Version No.:	1.1	Document Date:	05-May-2021

patients were randomized to it. Arm 2 continued until all 681 patient outcomes were recorded and did not hit either decision boundary. This is illustrated in Figure 3.

An alternative form of Bayesian data monitoring is an examination of the posterior densities of the different p_i parameters ($i \in \{\text{Control}, 1, 2, 3\}$) over time as in Figure 3, starting from a uniform prior reflecting ignorance, and with centers that change over time and with reduced uncertainty, as more evidence is gathered.

Table 3 also records the proportion of patient outcomes out of the maximum number of 681 that were recorded in the trial, as well as the final decision (efficacious/non-efficacious) and a 95% interval estimate of the relative risk reduction, based on the relationship (2).

Table 6: Data and Bayesian Analysis of a Single Simulated Trial

[figure not shown]
Arm	Analysis 1 events	Analysis 2 events	Analysis 3 events	Analysis 4 events	Stopping Reason	% patients	Pr(Efficacy Data)	Efficacy	RRR
1	15	28	45		Early efficacy	75.3	98.60%	Yes	36.3% [9.3%; 55.9%]
2	21	44	67	90	Enrolled all	100	52.60%	No	1.0% [-30.6%; 24.2%]
3	28	56			Futility	50.2	15.90%	No	-23.5% [-78.2%; 11.7%]
Control	22	45	71	91		100			

Statistical Analysis Plan

Sponsor:	McMaster University		
Protocol:	TOGETHER trial		
Document Version No.:	1.1	Document Date:	05-May-2021

Figure 3: the evolution of the posterior density of the event rate of each arm by interim analysis for the simulated example and posterior efficacy of all active arms by interim analysis*

*The dashed lines mark the decision boundaries.

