3. SUBJECT POPULATIONS

3.1. Population Definitions

The following subject populations will be evaluated and used for presentation and analysis of the data:

- Intent-to-treat (ITT) Population: The ITT Population includes all randomized patients.
- Per-protocol (PP) Population: Randomized patients who adhered to more than 80% of the assigned therapy.
- Safety Population: Randomized patients who received at least 1 dose of study medication.

The ITT Population is typically the primary population for the analysis of efficacy parameters. A subset of efficacy parameters will be evaluated for the PP population (see Section 4.6).

The Safety Population is typically the primary population for the analysis of safety endpoints.

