4. STATISTICAL METHODS

4.1. Sample Size Justification

The sample size of 681 patients per arm has been chosen for each experimental group to achieve 80% power with 0.05 two-sided Type 1 error for a pairwise comparison against the control to detect minimum treatment efficacy defined by 37.5% relative risk reduction (RRR) of preventing hospitalization assuming a control event rate (CER) of 15%.

Statistical Analysis Plan

Sponsor:	McMaster University		
Protocol:	TOGETHER trial		
Document Version No.:	1.1	Document Date:	05-May-2021

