4.2.6. Withdrawals, Dropouts, Loss to Follow-up

Subjects who withdrew from the study will not to be replaced.

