4.2.7. Missing, Unused, and Spurious Data

All data recorded on the CRF will be included in data listings that will accompany the clinical study report. Due to the design of the study and retention activities, we expect to be able to measure outcomes on all or the vast majority of participants. Multiple imputation will be employed where statistical models require adjustment for baseline covariates with up to 20% missing values. No multiple imputation of outcomes will be performed.

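### The decision rule defines its denominator as patients randomised but times its looks by recorded outcomes, and no rule covers an arm with fewer than 681 outcomes

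*SAP*

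**What the plan says.** **Denominator.** The SAP appendix models the events in each arm as binomial and says that n_ij "is the number of patients randomized to the" arm in question. The posterior is Beta(a + y, b + n − y) with a = b = 1. It feeds the posterior probability of efficacy that decides every stop and the final claim.

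**Timing of the looks.** The same appendix sets the interim looks at 171, 342 and 513 recorded outcomes per arm, described as quarters of maximum enrolment, "and a final analysis when all 681 patient outcomes have been registered". Section 4.3 also counts outcomes, and so does the worked example.

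**Missing outcomes.** Section 4.2.6 has one rule: "Subjects who withdrew from the study will not to be replaced". Section 4.2.7 expects outcomes on all or nearly all participants and adds: "No multiple imputation of outcomes will be performed". No other rule is given for a patient whose 28-day primary outcome is unknown.

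**Population.** Section 3.1: "The ITT Population includes all randomized patients".

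**Sample size.** Section 4.1 says that "681 patients per arm has been chosen for each experimental group to achieve 80% power with 0.05 two-sided Type 1 error" and states no allowance for withdrawal.

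**The concern.** Randomised patients and recorded outcomes are the same number only if nobody is lost. Once someone is, the SAP gives two answers for n.

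Taken literally, the definition puts a patient who leaves before Day 28 with no recorded event into n − y, that is, among the non-events. The arm that loses more patients then looks better than it is. The outcome-based wording avoids this, but it requires 681 outcomes from at most 681 enrolled without replacement, and one loss makes that impossible.

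The quantity affected is the one that stops arms and declares efficacy. If the SAP does not fix it, the denominator may be chosen after the data have been seen.

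**Working it through.** **1. The plan's own figures.** The worked example (Table 6) gives 75.3% and 50.2% of patients. These are 513/681 = 75.3% and 342/681 = 50.2%, so the example counts outcomes. Arm 1 there has 45 events against 71 in control, with a stated RRR of 36.3% [9.3%; 55.9%]. Beta(1,1) posteriors give 36.3% [10.0%; 55.4%] with n = 513 and 36.3% [9.5%; 55.6%] with n = 681. The interval cannot show which denominator was used.

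**2. Can the final trigger be met?** If each patient is lost with probability d, one arm has all its outcomes with probability (1 − d)^681.

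| d (assumed) | chance of 681 outcomes in one arm |
|---|---|
| 0.1% | 51% |
| 0.5% | 3.3% |
| 1% | 0.1% |
| 2% | practically zero |

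**3. Effect of n = randomised on false positives.** Inputs from the SAP: 681 per arm, control rate 15%, threshold 97.6%. Assumed: a drug with no effect; a share d of each arm lost, unrelated to outcome, with the events of those patients unseen; a single look at 681. The rate that the rule sees is 0.15(1 − d). With p1 for drug and p0 for control,

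false-positive rate ≈ 1 − Φ(1.977 − (p0 − p1)/SE), SE = √{[p1(1 − p1) + p0(1 − p0)]/681},

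where 1.977 is the normal quantile of 0.976.

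- No loss, or equal loss: the shift is 0 and the result is 2.4%.
- 5% drug, 2% control: p1 = 0.1425, p0 = 0.1470, SE = 0.0191, shift 0.236. Result 1 − Φ(1.741) = 4.1%.
- 8% drug, 2% control: p1 = 0.1380, p0 = 0.1470, SE = 0.0189, shift 0.475, apparent RRR 6.1%. Result 1 − Φ(1.502) = 6.7%.
- 2% drug, 5% control: shift −0.236. Result 1 − Φ(2.213) = 1.3%.

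Summing over both binomial distributions with exact Beta posteriors gives 2.4%, 4.1%, 6.6% and 1.3%. Simulation gives 4.0%, 6.6% and 1.4% for the three unequal cases, the same within simulation error.

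**4. The same cases with n = known outcomes.** Each arm now has 681(1 − d) patients at a true rate of 15%. The exact result is 2.4% in all of them, so the denominator alone causes the change in step 3.

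**5. When those lost are at higher risk.** Give them twice the event risk (30%) in both arms, with 8% lost on drug and 2% in control.

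- n = randomised: p1 = 0.15 − 0.08 × 0.30 = 0.126 and p0 = 0.15 − 0.02 × 0.30 = 0.144. The RRR is 12.5% and the false-positive rate 15.6%.
- n = known: 0.126/0.92 = 0.1370 and 0.144/0.98 = 0.1469. The RRR is still 6.8% and the false-positive rate 7.1%.

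**6. Four looks.** Simulating the stated thresholds at all four looks gives a baseline type I error of 5.95%, not the 2.5% in Table 4. That is a separate matter, so only the change is informative here. With n = randomised it becomes 8.5% (5% vs 2%), 11.0% (10% vs 5%) or 4.1% (2% vs 5%). With n = recorded outcomes it stays at 5.9% to 6.1%. With equal loss of up to 20% the two denominators differ by about one point of power (83.4% against 84.3% at 20%).

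**The case against.** A reader might infer that every withdrawal must either be scored as event-free or block the final analysis. The SAP does not support that. A complete-case reading, with n as recorded outcomes, fits section 4.3, the look triggers and the worked example; one phrase in the notation stands against it. Taken literally at an interim look, that phrase would also score patients still inside their 28 days as event-free, which outcome-based triggers are plainly meant to avoid. Section 4.2.7 excludes only multiple imputation, and nowhere does the SAP plan to set a missing outcome to no event. In the patient-level logistic model of 4.2.3.1, a patient without an outcome would naturally drop out.

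Nor does withdrawal equal a missing outcome. Only patients lost before Day 28 without a recorded event matter. The schedule of activities provides remote visits and an early-termination assessment, and the SAP expects few losses.

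It would also be wrong to put the 15.6% of step 5 down to the denominator. About half of that apparent RRR (6.8 of 12.5 points) is informative dropout and remains under either definition.

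All of this stands, and it limits the point. It does not remove it: the complete-case reading contradicts the written definition of n_ij, and it still leaves the final trigger unreachable after one loss. Two other routes do not help. The re-assessment in 4.3.1 may change the number but supplies no rule for a shortfall. And although 681 exceeds the 530 per arm that the inputs of 4.1 need for 80% power (two-sided 0.05, 15% vs 9.375%), the SAP does not call the surplus a dropout allowance, and the trigger asks for all 681 outcomes.

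**Conclusion.** The point holds as an internal contradiction plus a missing rule. The denominator is described in two ways, and nothing says what happens when 681 enrolled patients yield fewer than 681 outcomes.

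The size depends on withdrawal rates that the SAP does not give. Equal loss produces no bias under the null. Unequal loss unrelated to outcome, with n = randomised, moves the one-look false-positive rate from 2.4% to about 4% or 6.6% when the drug arm loses more (5% or 8% against 2%), and down to about 1.3% when control loses more (2% against 5%). These figures give each lost patient the full 15% event risk after leaving, so they overstate the effect for patients who leave part-way through the 28 days.

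It should be corrected before unblinded data are used. It does not show that the trial's result would be biased, because the direction and amount of any imbalance are unknown.

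**What to change.** 1. In the appendix, define n_ij as the patients in arm i with a known Day-28 primary outcome: an event, or confirmed event-free.
2. Trigger each look when the first 171, 342, 513 or 681 patients randomised per arm have reached Day 28 or withdrawn. The final look can then take place without replacement. Use the same wording in section 4.3.
3. Keep the primary analysis without imputation of outcomes, and say in 4.2.7 that it uses randomised patients with a known outcome. Add a tipping-point sensitivity analysis that varies, by arm, the event rate assumed in patients with missing outcomes. Step 5 shows why: the complete-case denominator does not remove bias from informative dropout.

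The cost is a few sentences of SAP text, slightly fewer patients in the denominator at each look than the nominal number, and one extra sensitivity analysis.

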2.2. Randomization Methodology

Eligible participants will be randomized at an equal allocation ratio to study experimental intervention(s) or placebo. Individual randomization will be stratified by clinical site, by age (<50 years vs. ≥50 years), and time from onset of symptoms (<120 hours vs. ≥120 hours). The randomization sequence for each clinical site will be prepared by the unblinded statistician and will be sent to the unblinded pharmacist at each participating clinical site. Allocation of treatment assignment will be concealed from all other study personnel.

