4.2.3. Statistical Analysis Details

4.2.3.1. Bayesian inference for dichotomous outcomes with covariate adjustment

Here we may use the generalized linear model framework for binary outcome with the logistic link function, namely

$$y_i \sim \text{Binom}(1, p_i)$$

with

$$\log \frac{p_i}{1 - p_i} = x_i^T \beta + \gamma T_i,$$

using the same notations as before. Assigning a noninformative prior distribution $p(\beta, \gamma) \propto 1$, the logarithm of the posterior distribution (after some simple algebra) is given by

$$\begin{aligned} \log p(\beta, \gamma | \mathbf{y}) &= \log p(\beta, \gamma) + \sum_{i=1}^n \log p(y_i | \beta, \gamma) \\ &= \sum_{i=1}^n \{y_i(x_i^T \beta + \gamma T_i) - \log[1 + \exp(x_i^T \beta + \gamma T_i)]\}, \quad (1) \end{aligned}$$

and a random sample from $p(\beta, \gamma | \mathbf{y})$ may then be drawn using Markov Chain Monte Carlo (MCMC) such as the Metropolis-Hastings algorithm¹ using (5) or Gibbs sampling using any software for Hierarchical Bayesian modeling such as BUGS² or JAGS³. Inference on the treatment effect will then follow the same procedure as in the numeric case.

The treatment effects on dichotomous outcomes will be estimated using R.

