4.3. Interim Analyses

Three interim efficacy analyses are planned. Assuming a uniform prior assigned to the different event rates, a total sample size of 681 patients per arm, a CER of 15%, and a RRR equals to 37.5%, we will do an interim analysis after observing 25%, 50% and 75% of the maximum number of patient outcomes, as well as at the trial completion. The posterior efficacy threshold will be 97.6% and the futility threshold will be 20%, 40% and 60%. Intervention arms(s) showing a posterior probability of efficacy crossing either boundary, will be stopped for either reason. These superiority and futility thresholds were determined based on 200,000 simulation runs in which different values of the RRR were considered (0%, 20%, and 37.5%). A description of this interim analysis in an event-based Bayesian adaptive trial and accompanying illustrating example can be found in the appendix of this document.

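### The efficacy rule compares crude arm rates and omits the randomisation strata, while the adjusted logistic model is optional, lists no covariates and has no decision role

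*SAP*

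**What the plan says.** Section 2.2 of the SAP: "Individual randomization will be stratified by clinical site, by age (<50 years vs. ≥50 years), and time from onset of symptoms", with the onset cut at 120 hours, and "Eligible participants will be randomized at an equal allocation ratio to study experimental intervention(s) or placebo".

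Section 4.3: "The posterior efficacy threshold will be 97.6% and the futility threshold will be 20%, 40% and 60" per cent. The appendix gives the calculation. Each arm's event rate has its own beta posterior, with a = b = 1 "for beta prior distribution of all arms, corresponding to a uniform distribution". The decision quantity is the posterior probability that the active rate is below the control rate, "which can be handily calculated by drawing independent Monte Carlo samples from the posterior distributions of the two arms using (1"). The timing is "Perform interim analysis when 171, 342, and 513 patient outcomes have been recorded for each of the trial arms", with a final analysis at 681, where "The same test is conducted at the end of the trial if no early stopping rules are triggered". No stratum or covariate enters.

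Section 4.2.3.1 starts: "Here we may use the generalized linear model framework for binary outcome with the logistic link function". Its linear predictor has a covariate vector, but the covariates are never listed. For inference it defers to a numeric-outcome case that the SAP does not contain. Section 4.2.3.2 bases inference on a credible interval for the treatment coefficient and presents that as the general practice; this is a different criterion from the 97.6% posterior probability. Section 4.2.7 plans imputation of baseline covariates for adjusted models, so adjustment is expected. Section 4.6 says the two primary events form a composite and names no model.

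**The concern.** Two things follow from these sections.

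- **Variance.** Stratified allocation balances the arms within strata, which removes between-stratum variation from the true sampling variance of the arm difference. Independent beta posteriors for crude rates still count that variation. If the strata predict the outcome, the posterior of the difference is too wide and the probability of efficacy is pulled towards 50%.
- **Which analysis governs.** The stopping and success rule is crude, and an adjusted model is available at the analyst's option with unspecified covariates. Near the boundary the two can give different answers to the primary question, and nothing in the SAP says which prevails.

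**Working it through.** **Inputs from the SAP:** control event rate 15%; RRR 37.5% and 20%; looks at 171, 342, 513 and 681 per arm; efficacy threshold 97.6%; futility 20/40/60%; Beta(1,1) priors.

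**Inputs assumed, because the SAP gives no stratum event rates and no site count:** 10 sites; age odds ratio 1.5 to 3.0; onset odds ratio 0.9 to 0.7; site SD 0.3 to 0.6 on the logit scale; overall rate held at 15%.

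**Step 1, the plan's own figures.** Simulating the rule as written gives about 90.8% power at RRR 37.5%, 44% at 20%, and 6.0% one-sided error. Table 4 states 84.8%, 30.7% and 2.5%. Table 6 does not reproduce either: 45 against 71 events of 513 gives 99.5% (stated 98.6%). This is a separate problem, but the comparison below has to start from the rule as written.

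**Step 2, variance ratio.** V = E[p_s(1 − p_s)] / [p(1 − p)], averaged over strata s. The assumed strengths, weakest to strongest, give V = 0.985, 0.967, 0.947 and 0.925. The crude precision at 681 per arm then needs 681 × V patients: 681 × 0.985 = 671 and 681 × 0.925 = 630, so 10 to 51 fewer per arm.

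**Step 3, one look.** The threshold is z(0.976) = 1.977. The crude statistic has true standard deviation √V, so its error is 1 − Φ(1.977/√V), which is 2.3%, 2.2%, 2.1% and 2.0% against a nominal 2.4%. At 681 per arm the adjusted test gains 0.3 to 1.4 points of power at RRR 37.5% and 0.6 to 3.0 at RRR 20%.

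**Step 4, the four-look rule.** Normal approximation, 1,000,000 runs, threshold left at 97.6%, crude / adjusted:

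| V | One-sided error % | Power %, RRR 20% | Power %, RRR 37.5% |
|---|---|---|---|
| 1 | 6.1 / 6.1 | 44.6 / 44.6 | 90.8 / 90.8 |
| 0.985 | 5.9 / 6.1 | 44.4 / 45.0 | 91.0 / 91.2 |
| 0.967 | 5.7 / 6.1 | 44.2 / 45.6 | 91.1 / 91.6 |
| 0.947 | 5.4 / 6.1 | 44.0 / 46.2 | 91.3 / 92.1 |
| 0.925 | 5.1 / 6.1 | 43.7 / 46.9 | 91.5 / 92.6 |

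The differences are 0.2 to 1.1 points at RRR 37.5% and 0.6 to 3.2 at RRR 20%. A separate run with the strongest ratio at 0.924 gave 3.3, so I take 0.6 to 3.3 as the range.

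**Step 5, where the gain comes from.** With balance within strata the two statistics share a numerator and differ only by √V. The crude rule is then close to an adjusted rule with a stricter threshold. For V = 0.925 that threshold is Φ(1.977/√0.925) = 98.0%. The adjusted rule run at that value gives 5.1% error and 91.5% power, the same as the crude rule. In this approximation, nearly all of the gain is the recovery of unused error.

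**Step 6, at the boundary.** For V = 0.925, 1.977 × √0.925 = 1.90, which is a probability of 97.1%. A crude posterior between 97.1% and 97.6% fails, although the adjusted one would pass.

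**Step 7, sparse data at the first interim.** Expected control events are 171 × 0.15 ≈ 26.

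**The case against.** - **The SAP does contain an adjusted model.** A reader might infer that adjustment was overlooked; Sections 4.2.3.1 and 4.2.7 show otherwise. This objection stands against that reading. It leaves the defect that the model is optional, unspecified and not linked to the decision.
- **The test is valid.** A reader might infer that posterior probabilities are miscalibrated in a way that undermines the result. The documents do not support that. The error is in the conservative direction, and only if the strata are prognostic. At RRR 37.5% the crude rule's own power does not fall below its value without stratum effects (91.0-91.5% against 90.8%).
- **The simple rule has advantages.** A reader might infer that precision is given away for nothing. The conjugate rule needs no model fitting, gives the RRR directly, and is the rule for which the SAP says its thresholds were simulated. With about 26 control events at the first interim, a flat-prior model with many site terms could be unstable. A simple decision test alongside an adjusted estimate can be defended if the SAP says so; it does not.
- **Adjustment at an unchanged threshold raises the error rate,** from 5.9-5.1% to about 6.1%. This stands, so the threshold has to be recalibrated as part of any change.

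The case for adjusting survives in this form: the adjusted rule's error stays at about 6.1% whatever the stratum strength, whereas the crude rule's depends on a strength nobody knows in advance. A threshold simulated without strata therefore carries over to the adjusted analysis but is too strict for the crude one.

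**Conclusion.** The point holds as a moderate weakness. The rule that decides efficacy at every look omits the three stratification factors, and the SAP does not say how that decision relates to the adjusted model it also describes. The text alone establishes this.

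The size rests on assumed stratum strength, applied equally in both arms, and on balance within strata. Over the assumed range the loss is small at the design effect and modest at RRR 20%; with weakly prognostic strata it is close to nil. A reader might also infer that adjusting would bring the design back to its stated 2.5% error. It would not: the adjusted four-look rule still runs at about 6%.

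**What to change.** - **Name one governing primary analysis,** at least for the final analysis: the logistic model with treatment, age stratum and onset stratum as fixed effects and site as a random intercept. State the decision criterion in that model, and replace the reference to the absent numeric case.
- **Use proper, weakly informative priors.** The flat prior in Section 4.2.3.1 is improper in any case. The practical danger is an improper posterior under separation, which a site with no events would cause if site were a fixed effect.
- **Say what the interims use:** the same model, or the beta-binomial rule because events are few at the first look.
- **Report the RRR from standardised predicted risks,** and keep the beta-binomial result as a sensitivity analysis.
- **Re-simulate the efficacy threshold** for the chosen model or combination of models, since leaving it at 97.6% raises the error rate.

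The cost is SAP text, model fitting at each look that uses the model, and a new simulation. No new data are needed, because the strata are recorded at randomisation. The failure of Table 4 to reproduce needs its own correction; the same simulation exercise could serve both.

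### Tables 4 and 5 of the SAP appendix treat the same 6.6% to 8.3% of simulated arms both as stopped early and as fully enrolled, so the printed operating characteristics contradict each other

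*SAP*

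**What the plan says.** The design is in the SAP appendix, under the proposed design for a 4-arm trial.

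- **Looks:** "Perform interim analysis when 171, 342, and 513 patient outcomes have been recorded for each of the trial arms", and "a final analysis when all 681 patient outcomes have been registered".
- **Efficacy:** "Stop early for efficacy if the posterior probability of efficacy exceeds 97.6" per cent.
- **Futility:** "Stop early for futility if the posterior probability of efficacy is smaller than 20% in the first analysis; 40% in the second analysis; 60" per cent at the third.
- **Prior:** "Use $a = b = 1$ for beta prior distribution of all arms, corresponding to a uniform distribution".
- **Scenario:** Section 4.3 assumes "a CER of 15%, and a RRR equals to 37.5" per cent, and RRRs of 0% and 20% were simulated as well.

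No third reason for ending an arm early is given. In the appendix's worked example, the arm that meets neither boundary runs to 681 outcomes.

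Table 4 is introduced with "The operating characteristics of this design, as determined by 200,000 simulation runs, are as follows" and gives power, mean (SD) percentage of patients, and cumulative stopping probabilities. Table 5 is introduced with "The simulation run also allows us to evaluate the frequency of the reasons for early stopping under each scenario" and splits each analysis into early efficacy, futility and 'None'.

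**The concern.** Under these rules, an arm that crosses no boundary at looks 1 to 3 goes on to the final analysis, so 'None' should be possible only at Analysis 4. Table 5 has non-zero 'None' entries at Analysis 2 (1.7% to 1.9%) and Analysis 3 (4.9% to 6.4%), and the SAP does not explain them.

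These tables are the plan's evidence for how the adaptive design behaves, and Section 4.3 says the thresholds were chosen from the simulations. If the entries are only misplaced, the printed early-stopping probabilities are wrong. If the program really ended those arms, the simulated design differs from the one in the plan. The other columns from that run, power and type I error included, would then describe a different design too.

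**Working it through.** **Inputs.** The look fractions are 171/681 = 25.11%, 342/681 = 50.22%, 513/681 = 75.33% and 100%. The other inputs are the printed cells of Tables 4 and 5.

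**Step 1: Table 4 against itself.** Let P1, P2 and P3 be the cumulative stopping probabilities. The mean percentage of patients is then fixed:

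mean = 100 − 25.11 × (P1 + P2) − 24.67 × P3, where 24.67 = 100 − 75.33.

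- RRR 37.5%: 100 − 25.11 × (0.252 + 0.535) − 24.67 × 0.738 = 62.0. Table 4 prints 64.1.
- RRR 20%: 100 − 25.11 × (0.104 + 0.239) − 24.67 × 0.392 = 81.7. Table 4 prints 84.2.
- RRR 0%: 100 − 25.11 × (0.168 + 0.425) − 24.67 × 0.670 = 68.6. Table 4 prints 71.1.

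Each printed probability is rounded to within 0.05 points, which moves the computed mean by at most 0.05 × (0.2511 + 0.2511 + 0.2467) = 0.04. The Monte Carlo standard error of the mean is about 28.4/√200,000 = 0.06. Neither explains gaps of 2.1 to 2.5 points, all in the same direction.

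**Step 2: the cells responsible.** The 'None' entries at Analyses 2 and 3 in Table 5 are:

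- RRR 37.5%: 1.7 + 4.9 = 6.6%
- RRR 20%: 1.8 + 6.3 = 8.1%
- RRR 0%: 1.9 + 6.4 = 8.3%

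All cells together sum to 100.1%, 99.9% and 100.0%, so each scenario is complete to rounding.

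**Step 3: cumulative stops (<=2 / <=3) rebuilt from Table 5.**

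| RRR | Table 4 | Efficacy + futility + 'None' | Efficacy + futility only |
|---|---|---|---|
| 37.5% | 53.5 / 73.8 | 53.5 / 73.9 | 51.8 / 67.3 |
| 20% | 23.9 / 39.2 | 23.7 / 39.0 | 21.9 / 30.9 |
| 0% | 42.5 / 67.0 | 42.5 / 67.1 | 40.6 / 58.8 |

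For example, at RRR 37.5% efficacy and futility by look 3 give (24.7 + 26.4 + 15.3) + (0.5 + 0.2 + 0.2) = 67.3. Adding 6.6 gives 73.9. Table 4 is reproduced only when the 'None' arms count as stopped. Without them the gaps at <=3 are 6.5, 8.3 and 8.2 points, and at <=2 they are 1.7, 2.0 and 1.9 points.

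**Step 4: mean (SD) % of patients rebuilt from Table 5.**

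| RRR | Table 4 | 'None' arms at 100% | 'None' arms at their listed look |
|---|---|---|---|
| 37.5% | 64.1 (29.6) | 64.1 (29.6) | 62.0 (28.2) |
| 20% | 84.2 (26.0) | 84.3 (26.0) | 81.8 (26.0) |
| 0% | 71.1 (28.4) | 71.1 (28.4) | 68.6 (27.2) |

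For example, at RRR 0% with the 'None' arms at 100%: 0.168 × 25.11 + 0.238 × 50.22 + 0.182 × 75.33 + 0.412 × 100 = 71.1. Here Table 4 is reproduced only when the same arms count as fully enrolled.

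**Step 5: can the printed Table 5 supply the corrected values?** The stated rules were simulated with Beta(1,1) priors, a control event rate of 15%, the looks and thresholds above, and 400,000 runs per scenario.

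| RRR | Stop <=2 / <=3, simulated | Table 4 | Power, simulated | Power, Table 4 |
|---|---|---|---|---|
| 37.5% | 65.3 / 83.3 | 53.5 / 73.8 | 90.9 | 84.8 |
| 20% | 33.9 / 50.8 | 23.9 / 39.2 | 44.3 | 30.7 |
| 0% | 46.9 / 68.3 | 42.5 / 67.0 | 5.9 | 2.5 |

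The stated rules do not reproduce the printed tables. The efficacy-plus-futility sums by look 3 (67.3, 30.9, 58.8) lie further from the simulated values than Table 4 does in every scenario.

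**The case against.** The strongest reply is that the contradiction has no known direction. A reader might infer that early stopping is overstated by up to 8.3 points. That is only one of two readings: if the arms did stop at looks 2 and 3, the stopping columns are right and the mean enrolment is wrong. Measured against the rules as written, the simulation puts early stopping above Table 4, not below it. This part of the objection stands, and overstatement cannot be asserted.

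A second reply is that little depends on these cells. The text under Table 4 draws two conclusions: a 2.5% one-sided type I error, and roughly two-thirds of the maximum sample size at RRR 37.5%. Neither quotes the disputed probabilities, and the second holds loosely at 64.1% or 62.0%. The sample size and decision rules do not change. The SAP also does not tie these probabilities to supply or accrual planning, so no such consequence should be claimed. This limits the weight of the point but does not remove it.

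A third reply is that the simulator may have followed a different schedule, for instance by passing the accrual of dropped arms to the remaining ones. An arm could then reach 681 by a trial-level third look. A trial of that idea produced 'None' entries at look 3 but none at look 2, and did not match the table. The SAP also defines its looks per arm. The cause remains unknown.

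**Conclusion.** The inconsistency is established from the printed cells alone. Two sets of columns in Table 4 treat the same 6.6%, 8.1% and 8.3% of arms in opposite ways. One of the following must hold:

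- the arms were fully enrolled, and Pr(Stop at <=3) exceeds Table 5's efficacy and futility stops by 6.5, 8.3 and 8.2 points; or
- the arms did stop, mean enrolment should read about 62.0, 81.8 and 68.6 instead of 64.1, 84.2 and 71.1, and the program contained a stopping rule that the plan does not list.

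The SAP does not show which. The result assumes only that looks fall at 171, 342, 513 and 681 outcomes per arm and that efficacy and futility are the only early stops, both as stated. It does not depend on which efficacy threshold generated the tables. It is an error in the stated operating characteristics that should be corrected. It does not in itself alter the primary analysis or the decision rules.

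**What to change.** Check the simulation program and remove any branch that ends an arm at look 2 or 3 without a boundary crossing. Rerun under the rules as stated (97.6% for efficacy; 20/40/60% for futility; looks at 171/342/513/681). Restate every column of Tables 4 and 5 from that one run, so that 'None' occurs only at Analysis 4 and Table 4's stopping columns equal the cumulative efficacy and futility stops of Table 5. Update the sentences under Table 4 if their figures change.

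Do not simply move the 'None' entries or insert 67.3, 30.9 and 58.8: these reconcile the printed tables with each other but do not describe the stated design.

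The cost is one rerun of existing code and two corrected tables. No patients are affected.
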